10.3.4. Reporting of SAEs

SAE Reporting to Pfizer Safety via an Electronic Data Collection Tool

- The primary mechanism for reporting an SAE to Pfizer Safety will be the electronic data collection tool.
- If the electronic system is unavailable, then the site will use the paper SAE data collection tool (see next section) to report the event within 24 hours.
- The site will enter the SAE data into the electronic system as soon as the data become available.
- After the study is completed at a given site, the electronic data collection tool will be taken off-line to prevent the entry of new data or changes to existing data.
- If a site receives a report of a new SAE from a study participant or receives updated data on a previously reported SAE after the electronic data collection tool has been taken off-line, then the site can report this information on a paper SAE form (see next section) or to Pfizer Safety by telephone.

SAE Reporting to Pfizer Safety via CT SAE Report Form

- Facsimile transmission of the CT SAE Report Form is the preferred method to transmit this information to Pfizer Safety.
- In circumstances when the facsimile is not working, notification by telephone is acceptable with a copy of the CT SAE Report Form sent by overnight mail or courier service.
- Initial notification via telephone does not replace the need for the investigator to complete and sign the CT SAE Report Form pages within the designated reporting time frames.

10.4. Appendix 4: Contraceptive and Barrier Guidance

10.4.1. Male Participant Reproductive Inclusion Criteria

Male participants are eligible to participate if they agree to the following requirements during the intervention period and for at least 28 days after the last dose of study intervention, which corresponds to the time needed to eliminate reproductive safety risk of the study intervention(s):

- Refrain from donating sperm.

PLUS either:

- Be abstinent from heterosexual intercourse with a female of childbearing potential as their preferred and usual lifestyle (abstinent on a long-term and persistent basis) and agree to remain abstinent.

OR

- Must agree to use contraception/barrier as detailed below:
 - Agree to use a male condom when having sexual intercourse with a woman of childbearing potential who is not currently pregnant.
 - In addition to male condom use, a highly effective method of contraception may be considered in WOCBP partners of male participants (refer to the list of highly effective methods below in [Section 10.4.4](#)).

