5.1. Inclusion Criteria

Participants are eligible to be included in the study only if all of the following criteria apply:

Age and Sex:

1. Female participants of non-childbearing potential and/or male participants must be 18 to 55 years of age, inclusive, at the time of signing the ICD.
 - Refer to [Appendix 4](#) for reproductive criteria for male ([Section 10.4.1](#)) and female ([Section 10.4.2](#)) participants.

Type of Participant and Disease Characteristics:

2. Male and female participants who are overtly healthy as determined by medical evaluation including a detailed medical history, complete physical examination, vital signs which include BP, temperature and pulse rate measurement, clinical laboratory tests, and ECG.
3. Participants who are willing and able to comply with all scheduled visits, treatment plan, laboratory tests, lifestyle considerations, and other study procedures.

Weight:

4. BMI of 17.5 to 30.5 kg/m²; and a total body weight >50 kg (110 lb).

Informed Consent:

5. Capable of giving signed informed consent as described in [Appendix 1](#), which includes compliance with the requirements and restrictions listed in the ICD and in this protocol.

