5.2. Exclusion Criteria

Participants are excluded from the study if any of the following criteria apply:

Medical Conditions:

1. Evidence or history of clinically significant hematological, renal, endocrine, pulmonary, gastrointestinal (eg, ulcerative colitis, irritable bowel syndrome, Crohn's disease), cardiovascular, hepatic, psychiatric, neurological, dermatological, or allergic disease (including drug allergies, but excluding untreated, asymptomatic, seasonal allergies at the time of dosing).
2. Any condition possibly affecting drug absorption (eg, gastrectomy, cholecystectomy).

3. History of HIV infection, hepatitis B, or hepatitis C; positive testing for HIV, HBsAg, HBcAb or HCVAb. As an exception, a positive HBsAb as a result of participant vaccination is permissible.
4. Other medical or psychiatric condition including recent (within the past year) or active suicidal ideation/behavior or laboratory abnormality that may increase the risk of study participation or, in the investigator's judgment, make the participant inappropriate for the study.
5. A history of hypersensitivity to the active compounds or to any inactive ingredients (excipients) contained in the formulations of bosutinib.

Prior/Concomitant Therapy:

6. Use of prescription or nonprescription drugs and dietary and herbal supplements within 7 days or 5 half-lives (whichever is longer) prior to the first dose of study intervention.
Proton pump inhibitors must be discontinued at least 14 days prior to the first dose of study medication.
Hormone replacement therapy must be discontinued at least 28 days prior to the first dose of study medication.

Refer to [Section 6.8](#) for additional details.

Prior/Concurrent Clinical Study Experience:

7. Previous administration with an investigational drug within 30 days (or as determined by the local requirement) or 5 half-lives preceding the first dose of study intervention used in this study (whichever is longer).

Diagnostic Assessments:

8. A positive urine drug test.
9. Screening supine BP ≥ 140 mm Hg (systolic) or ≥ 90 mm Hg (diastolic), following at least 5 minutes of supine rest. If BP is ≥ 140 mm Hg (systolic) or ≥ 90 mm Hg (diastolic), the BP should be repeated 2 more times and the average of the 3 BP values should be used to determine the participant's eligibility.

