10. Baseline 12-lead ECG that demonstrates clinically relevant abnormalities that may affect participant safety or interpretation of study results (eg, baseline QTcF interval >450 msec, complete LBBB, signs of an acute or indeterminate-age myocardial infarction, ST-T interval changes suggestive of myocardial ischemia, second or -third-degree AV block, or serious bradyarrhythmias or tachyarrhythmias). If the baseline uncorrected QT interval is >450 msec, this interval should be rate-corrected

using the Fridericia method and the resulting QTcF should be used for decision making and reporting. If QTcF exceeds 450 msec, or QRS exceeds 120 msec, the ECG should be repeated 2 more times and the average of the 3 QTcF or QRS values should be used to determine the participant's eligibility. Computer-interpreted ECGs should be overread by a physician experienced in reading ECGs before excluding a participant.

11. Participants with **ANY** of the following abnormalities in clinical laboratory tests at screening, as assessed by the study-specific laboratory and confirmed by a single repeat test, if deemed necessary:
 - eGFR (CKD-EPI) < 90
 - AST **or** ALT level $\geq 1.5 \times$ ULN;
 - Total bilirubin level $\geq 1.5 \times$ ULN; participants with a history of Gilbert's syndrome may have direct bilirubin measured and would be eligible for this study provided the direct bilirubin level is \leq ULN.

Other Exclusions:

12. History of alcohol abuse or binge drinking and/or any other illicit drug use or dependence within 6 months of Screening. Binge drinking is defined as a pattern of 5 (male) and 4 (female) or more alcoholic drinks in about 2 hours. As a general rule, alcohol intake should not exceed 14 units per week (1 unit = 8 ounces [240 mL] beer, 1 ounce [30 mL] of 40% spirit or 3 ounces [90 mL] of wine).
13. Use of tobacco/nicotine containing products in excess of the equivalent of 5 cigarettes/day.
14. Male participants with partners currently pregnant; male participants who are unwilling or unable to use a highly effective method of contraception as outlined in this protocol for the duration of the study and for at least 28 days after the last dose of IP.
15. Blood donation (excluding plasma donations) of approximately 1 pint (500 mL) or more within 60 days prior to dosing.
16. Unwilling or unable to comply with the criteria in the **Lifestyle Considerations** section of this protocol.

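### Section 10.4.1 makes a highly effective contraceptive method optional for men, while Section 4.2 and exclusion 14 make it a condition of entry

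*Protocol*

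**What the plan says.** Two groups of Protocol passages describe what a male participant must do.

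**The Appendix 4 rule.** Inclusion criterion 1 (Section 5.1) refers the reader to Section 10.4.1 for the male reproductive criteria. That section opens by saying which men are eligible. Every man must "Refrain from donating sperm". In addition he must either be abstinent or accept contraception. Under the contraception branch the one mandatory item is: "Agree to use a male condom when having sexual intercourse with a woman of childbearing potential who is not currently pregnant". The next item says that, on top of the condom, "a highly effective method of contraception may be considered in WOCBP partners of male participants".

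**The rule elsewhere.** Exclusion 14 (Section 5.2) bars "male participants who are unwilling or unable to use a highly effective method of contraception as outlined in this protocol", with a minimum period running "for at least 28 days after the last dose of IP". Section 4.2 states that a highly effective method is mandatory for men with female partners who could become pregnant, and cites Appendix 4 for it. The risk table in Section 2.3.1 gives the same exclusion as part of the mitigation of fetal risk, again citing Appendix 4. Section 5.3.4 has the investigator confirm a method from the Section 10.4.4 list and tell the participant that highly effective contraception is needed.

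The SAP contains no contraception criteria and does not settle the point.

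**The concern.** One passage presents the highly effective method as something to think about; others present it as a condition of taking part. Both cannot describe the same obligation. The weaker wording stands in the section whose title and cross-reference mark it as the male inclusion rule.

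The protocol says in Section 4.2 that bosutinib can cause fetal harm. Women of childbearing potential cannot enrol, so contraception by male participants and their partners carries much of the remaining mitigation in the risk table. A site that treats Section 10.4.1 as the operative rule, as inclusion 1 invites, could enrol or counsel a man who relies on a condom alone. That would breach exclusion 14, and it could not be approved in advance, because Section 5 does not allow waivers of enrolment criteria.

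**Working it through.** No statistical calculation applies. The check sets the passages side by side and asks whether any reading makes them agree.

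**Step 1: status of a highly effective method for a non-abstinent man whose partner could become pregnant.**

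| Protocol section | Condom | Highly effective method |
|---|---|---|
| 10.4.1 (cited by inclusion 1) | Mandatory | Optional, in addition to the condom |
| 4.2 (rationale) | Not mentioned | Mandatory |
| 5.2, exclusion 14 | Not mentioned | Unwilling or unable means excluded |
| 2.3.1 (risk table) | Not mentioned | Unwilling or unable means excluded |
| 5.3.4 (counselling) | Not mentioned | Participant told that it is needed |

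**Step 2: could the condom itself be the highly effective method?** Exclusion 14 points to what the protocol outlines, which might be taken to mean Appendix 4. Section 10.4.4 has 5 low-user-dependency methods (items 1 to 5) and 3 user-dependent methods (items 6 to 8), so 5 + 3 = 8 highly effective methods. The condom is 0 of the 8. It appears only among the barrier options: the male condom is named in 2 of the 3, and these are to be added to the user-dependent methods. Section 10.4.1 also keeps the two apart by placing the highly effective method on top of condom use. This reading therefore fails.

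**Step 3: apply the criteria to three kinds of men, each refraining from sperm donation.**

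| Man | Section 10.4.1 | Exclusion 14 |
|---|---|---|
| Abstinent | Met | Not engaged: abstinence is item 8 of the Section 10.4.4 list |
| Condom plus a highly effective method | Met | Not engaged |
| Condom only, declines a highly effective method | Met | Barred |

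The passages diverge only for the third man. No claim is made about the abstinence branch.

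**Step 4: combined effect.** Section 5.1 says: "Participants are eligible to be included in the study only if all of the following criteria apply". Section 5.2 says: "Participants are excluded from the study if any of the following criteria apply". Meeting Section 10.4.1 is therefore necessary but not sufficient, and the condom-only man is excluded when the whole set is applied.

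**Step 5: duration.** Both Section 10.4.1 and exclusion 14 give a minimum of 28 days after the last dose, a difference of 28 − 28 = 0 days. The period before that is worded differently: the intervention period in Section 10.4.1, the duration of the study in exclusion 14. This is a side point.

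**The case against.** The strongest reply is that the outcome is never in doubt. Any one exclusion bars entry, so exclusion 14 settles the matter whatever Section 10.4.1 says. A man can satisfy every passage at once by using a condom together with a highly effective method. The harm needs a site to follow one cross-reference and overlook an exclusion criterion. Other text works against that: Section 5.3.4 requires the conversation about highly effective contraception and the participant's affirmation to be documented, and the Schedule of Activities repeats the contraception check at screening, Day -1, Days 4, 5 and 7, follow-up and early termination. It can also be argued that Section 10.4.1 separates what the man does (condom) from what his partner may use, since most of the listed methods are used by the partner.

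Much of this stands. No deviation is forced, the safeguards are real, and they limit the seriousness of the point. They do not remove the conflict. Section 4.2 places the requirement on men with such partners and contains nothing that turns it into an option. The man-versus-partner distinction does not help, because Section 4.2 and exclusion 14 both ask for a highly effective method whoever uses it. The safeguards also leave the eligibility wording of Section 10.4.1 unchanged, and that is where inclusion 1 sends staff.

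**Conclusion.** The concern holds. Section 10.4.1 states a male eligibility rule that is weaker than Section 4.2, exclusion 14 and the protocol's own fetal-risk mitigation, and the cross-references to Appendix 4 do not reconcile them.

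Its reach is narrow: non-abstinent men with a partner of childbearing potential who accept a condom but not a highly effective method. The documents give no basis for counting them, and among approximately 18 participants there may be none. There is no effect on the PK estimates, the sample size or the confidence intervals. The point should be corrected because it concerns a safety rule that sites must apply at enrolment and at repeated checks. The conclusion rests on the current protocol wording and on Section 10.4.4 being the protocol's full list of highly effective methods.

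**What to change.** Reconcile Section 10.4.1 with Section 2.3.1, Section 4.2, exclusion 14 and Section 5.3.4, so that all state one contraception requirement for male participants. Which rule stands is for the sponsor's clinical team to decide; this review takes no position. The same edit can align the wording of the period before the 28-day minimum in Section 10.4.1 and exclusion 14.

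The cost is protocol wording only, either in Section 10.4.1 or in the passages it has to match. No procedure, visit or analysis is added, and the SAP needs no change.

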10.4.2. Female Participant Reproductive Inclusion Criteria

A female participant is eligible to participate if she is not a WOCBP (see definitions below in Section 10.4.3).

The investigator is responsible for review of medical history, menstrual history, and recent sexual activity to decrease the risk for inclusion of a WOCBP.

10.4.3. Woman of Childbearing Potential

A woman is considered fertile following menarche and until becoming postmenopausal unless permanently sterile (see below).

If fertility is unclear (eg, amenorrhea in adolescents or athletes) and a menstrual cycle cannot be confirmed before the first dose of study intervention, additional evaluation should be considered.

Women in the following categories are not considered WOCBP:

1. Premenopausal female with 1 of the following:

- Documented hysterectomy;
- Documented bilateral salpingectomy;
- Documented bilateral oophorectomy.

For individuals with permanent infertility due to an alternate medical cause other than the above, (eg, mullerian agenesis, androgen insensitivity), investigator discretion should be applied to determining study entry.

Note: Documentation for any of the above categories can come from the site personnel's review of the participant's medical records, medical examination, or medical history interview. The method of documentation should be recorded in the participant's medical record for the study.

2. Postmenopausal female.

- A postmenopausal state is defined as no menses for 12 months without an alternative medical cause. In addition:
 - A high FSH level in the postmenopausal range must be used to confirm a postmenopausal state in women under 60 years old and not using hormonal contraception or HRT.
 - A female on HRT and whose menopausal status is in doubt will be required to use one of the nonestrogen hormonal highly effective contraception methods if they wish to continue their HRT during the study. Otherwise, they must discontinue HRT to allow confirmation of postmenopausal status before study enrollment.

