4.2. Scientific Rationale for Study Design

The current study aims to compare the bioavailability of bosutinib when orally administered as capsule contents mixed with applesauce or yogurt to the oral administration of intact capsules in healthy participants under fed condition.

The study is being designed as a crossover study to account for any period effect. Between each sequential dosing of bosutinib, a minimum of 14-day washout is proposed to minimize any residual bosutinib concentrations prior to start of the next period, as bosutinib has a plasma elimination $t_{1/2}$ of approximately 34 hours.

Bosutinib is currently labeled to be administered with food for improved tolerability. Therefore, this study will be conducted under fed condition using a high-fat and high-calorie meal^{2,3}.

Based on findings from animal studies and its mechanism of action, bosutinib can cause fetal harm when administered to a pregnant woman; therefore, females of child-bearing potential will be excluded from the study. In addition, male participants with partners currently pregnant will be excluded and the use of a highly effective method of contraception is required for male participants with female partners of child bearing potential (see [Appendix 4](#)).

Retained Research Samples will be collected and stored for further analyses which may, for example, provide greater understanding of the study intervention.

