6.8. Concomitant Therapy

Use of prescription or nonprescription drugs and dietary and herbal supplements are prohibited within 7 days or 5 half-lives (whichever is longer) prior to the first dose of study intervention. Limited use of nonprescription medications that are not believed to affect participant safety or the overall results of the study may be permitted on a case-by-case basis following approval by the sponsor. Acetaminophen/paracetamol may be used at doses of ≤ 1 g/day.

Proton pump inhibitors must be discontinued at least 14 days prior to the first dose of study medication and is prohibited for the duration of the study.

Females taking hormone replacement therapy may be eligible to participate in this study if they are willing to discontinue therapy at least 28 days prior to the first dose of study treatment and remain off hormonal therapy for the duration of the study.

All concomitant treatments taken during the study must be recorded with indication, daily dose, and start and stop dates of administration. All participants will be questioned about concomitant treatment at each clinic visit.

Treatments taken within 28 days before the first dose of study intervention will be documented as a prior treatment. Treatments taken after the first dose of study intervention will be documented as concomitant treatments.

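### Appendix 4 lets a woman on HRT of doubtful menopausal status stay on it during the study, contradicting exclusion 6 and Sections 6.8 and 4.2; a site relying on the appendix could enrol her in error

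*Protocol*

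**What the plan says.** Female eligibility runs through Appendix 4. Inclusion 1 (Section 5.1) refers to Section 10.4.2, which states "A female participant is eligible to participate if she is not a WOCBP" and sends the reader to Section 10.4.3 for the definition.

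Section 10.4.3 lists the women who are not regarded as being of childbearing potential. Under its postmenopausal category it gives a woman on HRT with doubtful menopausal status two branches:

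- Under the first branch, she follows a contraception condition and keeps her HRT; the permitted methods are described as "nonestrogen hormonal highly effective contraception methods if they wish to continue their HRT during the study".
- Under the second branch, which applies to anyone not taking the first, HRT stops: "Otherwise, they must discontinue HRT to allow confirmation of postmenopausal status before study enrollment".

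Three other places in the protocol bear on the same woman:

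- Section 5.2, exclusion 6: "Hormone replacement therapy must be discontinued at least 28 days prior to the first dose of study medication". No exception is given.
- Section 6.8: "Females taking hormone replacement therapy may be eligible to participate in this study if they are willing to discontinue therapy at least 28 days" before the first dose, and if they "remain off hormonal therapy for the duration of the study".
- Section 4.2, giving fetal harm as the reason: "females of child-bearing potential will be excluded from the study".

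Appendix 4 does not refer to exclusion 6 or Section 6.8, and neither of those refers to the continuation branch. The SAP does not touch the point.

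**The concern.** The first branch in Section 10.4.3 and the rules in Sections 5.2 and 6.8 cannot both apply to the same woman. One permits HRT during the study and the others forbid it. The branch also sits inside the list of women treated as not of childbearing potential, although by its own terms it covers a woman whose status has not been settled.

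Two things are at stake. The first is the fetal-harm safeguard, which in this protocol rests on keeping women of childbearing potential out. The second is eligibility compliance. Section 5 bars waivers, so enrolling a woman under the continuation branch would be a protocol deviation that the protocol's own wording invited. A lesser matter is that HRT would be present as co-medication in an exposure comparison that was meant to be free of it.

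**Working it through.** No arithmetic applies. The only number involved, 28 days before the first dose, is the same in exclusion 6 and Section 6.8. The check is a comparison of the texts for one case: a woman within the 18 to 55 age range, on HRT, of doubtful menopausal status, who wants to continue HRT.

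| Place | May she stay on HRT during the study? | Must postmenopausal status be confirmed? |
|---|---|---|
| 10.4.3, first branch | Yes, with a specified contraceptive | Not required by this branch |
| 10.4.3, second branch | No | Yes, before enrolment |
| 5.2, exclusion 6 | No, stopped at least 28 days before first dose | Not addressed |
| 6.8 | No, stopped at least 28 days before and not resumed | Not addressed |
| 4.2 and 10.4.2 | Not addressed | She must not be of childbearing potential |

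**Step 1: HRT.** The first branch is incompatible with exclusion 6 and Section 6.8. The second branch is compatible with both. The conflict therefore lies in one branch of one bullet.

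**Step 2: menopausal status.** The second branch ties stopping HRT to confirmation of status. The first has no such step, so it leaves a woman of unconfirmed status within the postmenopausal category, contrary to the intent of Section 4.2.

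**Step 3: which text governs.** Section 5.2 opens with "Participants are excluded from the study if any of the following criteria apply". Meeting the Appendix 4 definition satisfies part of inclusion 1, but one exclusion criterion is enough to keep her out. A woman still on HRT fails exclusion 6.

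**Step 4: what would catch an error.** If a site applied Appendix 4 alone, the rest of the protocol offers little backstop:

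- The Schedule of Activities and Table 6 (Section 10.2) list no pregnancy test.
- The introduction to Section 10.4.4 speaks of contraception by men or by partners of male participants, not by female participants.
- Section 8.3.5.1 defines exposure during pregnancy for partners of male participants and for environmental exposure. It has no case for a pregnant female participant.
- Section 5.3.4 does tell participants to call if pregnancy is suspected, and contraception checks are scheduled, but neither settles menopausal status at entry.

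**The case against.** The strongest objection is that exclusion 6 already resolves the conflict. Entry requires every inclusion criterion and no exclusion criterion, waivers are barred, and Section 6.8 speaks directly to HRT users. On that view the continuation branch is an inoperative leftover and no woman gets in through it. This stands as far as the protocol's logic goes. A reader might infer that the protocol both admits and excludes the same woman, and the documents do not support that. It does not repair the text: Appendix 4 is where a site looks to decide childbearing potential, and there it finds permission to continue HRT with no pointer to the contrary rule.

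It can also be said that the branch states a contraception requirement without declaring her eligible, since Section 10.4.3 treats a woman as fertile until she is postmenopausal or permanently sterile. That reading is possible. The branch nevertheless appears within the list of women not considered to be of childbearing potential, so the opposite reading is at least as natural.

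Two further inferences should be resisted:

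- **That this is the only route that escapes FSH confirmation.** The FSH bullet in Section 10.4.3 leaves out every user of HRT or hormonal contraception, not just this woman. Footnote i of the Schedule of Activities calls for FSH at screening in women amenorrheic for at least 12 months, with no HRT exemption.
- **That the required contraceptive must be hormonal**, and so breaches Section 6.8 a second time. The phrase describing the method is ambiguous and matches no heading in Section 10.4.4, which also lists non-hormonal highly effective methods.

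**Conclusion.** The contradiction is real and confined to one bullet. An operative eligibility definition permits what exclusion 6 and Section 6.8 prohibit, and it covers a woman whose status Section 4.2 needs to be settled. The consequence is a risk of enrolment in error at a site relying on Appendix 4.

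The size is small. The documents do not say how many HRT users are expected, and in a study of approximately 18 participants run strictly to Section 5.2 the number entering this way would be none. Sample size, analysis sets and the mixed model are unaffected. The point deserves correction because it touches the fetal-harm safeguard.

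This rests on two assumptions: that the branch is read as part of the non-childbearing definition in which it is placed, and that no site instruction outside these documents already settles the matter.

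**What to change.** Reconcile the HRT bullet in Section 10.4.3 with exclusion 6 in Section 5.2, Section 6.8 and Section 4.2. After the change, a single rule on HRT should apply wherever it is mentioned, and the definition of non-childbearing potential should not cover a woman whose status is unconfirmed. A cross-reference from Appendix 4 to exclusion 6 and Section 6.8 would help keep the texts aligned. The sponsor decides what the rule is; this review takes no position on it.

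The cost is likely the edit of one bullet, through whatever amendment process applies. It needs no added tests or participants and no change to the SAP.
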